#### **8.1.5.2.5 Early termination (ET)/Unscheduled Visit (UV)**

A subject should attend an unscheduled visit if requested by the sponsor or the investigator. The assessments are at the investigator's discretion. At all unscheduled visits initiated for the purpose of confirming virologic failure.

The Sponsor and Promotor must be informed as soon as possible, when a subject comes off treatment due to an AE.

If a subject discontinues treatment early for any reason then the following assessments for the Early Termination (ET) Visit must be performed:

- Perform complete physical examination
- Obtain body weight
- Obtain vital signs
- Assessment of AEs and concomitant medications
- Obtain blood samples for :
  - Hematology and chemistry
  - Coagulation
  - HCV RNA
- Confirmation of birth control
- Obtain urine sample for :
  - Beta-HCG pregnancy test for females of childbearing potential only
- Complete medication pill count

### **8.1.5.3 Post Treatment Assessments**

The post treatment Week 4, 12 and 24 visits should be timed from the date of last administration of study drugs. All subjects must be complete the post treatment Week 4 and 12 visits. Subject with HCV RNA < LLOQ at the post treatment week 12 will complete the post treatment Week 24 visit, unless viral relapse is determined.

Female subjects of childbearing potential should be provided with Urine Pregnancy Test Kits, instructed on their use and requested to continue to self-monitor for pregnancy between scheduled study visits, every 4 weeks, for 6 months after their last dose of study drugs. If required by regulations, additional pregnancy test beyond 6 months may be added. The subject will be contracted every 4 weeks and asked to report results of the urine pregnancy tests.

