i) INR > 1.5 x ULN unless subject has known hemophilia or is stable on an anticoagulant regime affecting INR

3 - Chronic liver disease of a non-HCV etiology (e.g., hemochromatosis, Wilson's disease, alfa-1 antitrypsin deficiency, cholangitis)

4 - Infection with hepatitis B virus (HBV) or human immunodeficiency virus (HIV)

5 - Clinically-relevant alcohol or drug abuse within 12 months of Screening. A positive drug screen will exclude subjects unless it can be explained by a prescribed medication; the diagnosis and prescription must be approved by the investigator

6 - Use of any prohibited concomitant medication

7 - Known hypersensitivity to the study drug, the metabolites, or formulation excipient

**Study Procedures/  
Frequency :**

Screening assessments will be completed within 28 days of the Day 1 visit. The screening window can be extended to 42 days for subjects requiring a liver biopsy, or extenuating circumstances.

All subjects will complete the following study visits: Screening, Day 1, and on-treatment visits at the end of week 2, week 4 and week 8.

Posttreatment visits will occur at Weeks 4, 12, and 24 after last dose of study drug. All subjects will complete the posttreatment Week 4 and 12 visits. Subjects who achieve SVR12 (HCV RNA < LLOQ at posttreatment Week12) will complete the posttreatment Week 24 visit.

Screening assessments will include physical examination, medical history, height, weight, vital signs, adverse events related to screening procedures, concomitant medications, safety laboratory tests (including hematology, chemistry, and coagulation), HCV RNA, serology (HCV, HBV), serology and/or antigen testing for HIV, HCV genotyping, hemoglobin A1c (HbA1c), assessment of the absence of cirrhosis or severe fibrosis (including Fibrotest® and Fibroscan®), serum  $\beta$ -human chorionic gonadotropin ( $\beta$ -hCG) (females of child-bearing potential only), urinalysis.

On-treatment assessments include adverse events (AEs), concomitant medications, study medication dispensation and pill count, physical examination, weight, vital signs, safety laboratory tests, HCV RNA, and urine pregnancy tests (females of child bearing potential only).

Posttreatment assessments include Aes, concomitant medications, vital signs, safety laboratory tests (including hematology, chemistry, and coagulation), HCV RNA, and urine pregnancy tests (females of child-bearing potential only).

**Test Product, Dose,  
And Mode of  
Administration :**

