## 6. STUDY METHODOLOGY

### 6.1 Entry Criteria

#### 6.1.1 Primary endpoint

The primary efficacy endpoint is the proportion of subjects with SVR12 (HCV RNA < LLOQ 12 weeks after cessation of treatment) in the full analysis set

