#### **8.1.5.3.2 Post Treatment Week 12 and 24 (+ 5 days)**

The following procedures are to be completed 12 and 24 weeks after taking the last dose of study drugs :

- Obtain body weight
- Obtain vital signs
- Assessment of AEs only related to study procedure
- Concomitant medications
- Obtain blood samples for :  
HCV RNA
- Confirmation of birth control
- Obtain urine sample for :  
Beta-HCG pregnancy test for females of childbearing potential only

Subjects with HCV RNA < LLOQ at the post treatment Week 12 Visit will return for the Post treatment Week 24 Visit

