### **10.2 Statistical Analysis Plan Summary**

The analysis set for antiviral activity analyses will be the Full Analysis Set which includes subjects who were enrolled and received at least one dose of study drug and have naïve chronic genotype 1b HCV infection with non severe fibrosis.

Statistical analysis will be performed using Stata software (version 13; Stata-Corp, College Station, Tex., USA). All statistical tests will be two-sided and  $p < 0.05$  will be considered significant.

Qualitative variables will be described in terms of numbers and proportions.

Quantitative variables will be described in terms of numbers, mean  $\pm$  standard deviation or median [inter-quartile range] according to statistical distribution (normality studied using Shapiro-Wilk test).

Graphic representations will be complete presentations of results.

Sensitivity analyses will be considered to measure the possible impact of missing data on results and the more appropriate imputation method. For the analysis of post-baseline categorical efficacy endpoints, if a data point is missing and is immediately preceded and followed in time by values that are deemed successes, then the missing data point will be termed a success; otherwise the data point will be termed a failure. For example if a data point is missing and is preceded and followed in time by values that are <LLOQ target not detected (TND), then the missing data point will be set to < LLOQ TND.

Demographic and baseline measurements will be summarized using standard descriptive methods by treatment group and overall.

Exploratory analyses may be performed to assess the relationship between demographic, baseline characteristics, (including baseline viral load, age, sex, baseline ALT level, bodyweight, fibrosis score and additional endpoints as necessary) and antiviral activity (HCV RNA reduction, proportion of subjects with HCV RNA below the limit of quantification and target not detected at various time points during and following discontinuation of study drugs). Predictive factors of antiviral activities may be examined using regression type of analysis.

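### A subject who misses the week-12 sample has no scheduled week-24 visit, so the missing-data rule has no following value for SVR12 and defaults to failure

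*Combined protocol and SAP*

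**What the plan says.** **Endpoint.** Section 6.1.1: "The primary efficacy endpoint is the proportion of subjects with SVR12 (HCV RNA < LLOQ 12 weeks after cessation of treatment) in the full analysis". Section 10.2 defines the Full Analysis Set as enrolled subjects of the target population who took at least one dose, so a missing week-12 result stays in the denominator.

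**Missing-data rule.** Section 10.2 gives one general rule. Its scope is "For the analysis of post-baseline categorical efficacy endpoints", which includes SVR12. A missing point becomes a success "if a data point is missing and is immediately preceded and followed in time by values that are deemed successes"; "otherwise the data point will be termed a failure".

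**Follow-up schedule.** Section 8.1.5.3 makes two visits universal: "All subjects must be complete the post treatment Week 4 and 12 visits". Week 24 is treated differently: "Subject with HCV RNA < LLOQ at the post treatment week 12 will complete the post treatment Week 24 visit, unless viral relapse is determined". The synopsis has "Subjects who achieve SVR12 (HCV RNA < LLOQ at posttreatment Week12) will complete the posttreatment Week 24 visit", and section 8.1.5.3.2 has "Subjects with HCV RNA < LLOQ at the post treatment Week 12 Visit will return for the Post treatment Week 24 Visit".

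**Text without the condition.** The flow chart in section 7 marks HCV RNA at follow-up weeks 4, 12 and 24 and at unscheduled visits, and no footnote limits week 24 to week-12 responders. Section 8.1.5.2.5 allows unscheduled visits on request. Section 8.1.5.4 sends subjects who stop treatment early on to the follow-up visits and does not repeat the week-12 condition.

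**The concern.** The rule in 10.2 needs a result on each side of the gap. For a missing SVR12, the result before it is normally follow-up week 4 and the only scheduled result after it is week 24. Three places in the protocol make week 24 depend on the very result that is missing. Following them, a site has no instruction to bring back a subject whose week-12 sample was missed, lost or unusable. The success half of the rule then has nothing to work on, and the failure default applies to SVR12. With week 24 also uncollected, SVR24 becomes a failure too.

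Two things are at stake. First, the primary proportion can be lowered by missed samples in subjects whose response was in fact sustained. Second, because the flow chart carries no such condition, two identical patients can be classified differently according to which part of the protocol the site followed. A week-24 sample that was not drawn cannot be recovered at analysis.

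**Working it through.** **1. Rule against schedule, for each post-treatment endpoint**

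| Missing result | Next scheduled value | Who is scheduled for it (8.1.5.3) | Can a scheduled value bridge it? |
|---|---|---|---|
| Week 4 (SVR4) | Week 12 | All subjects | Yes |
| Week 12 (SVR12) | Week 24 | Subjects < LLOQ at week 12 | No: the condition cannot be met without a week-12 result |
| Week 24 (SVR24) | None | – | No |

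Under the written condition, a missing week 12 is followed by zero scheduled HCV RNA values. Two other routes can still supply one: an unscheduled sample, or a site working from the flow chart.

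**2. The plan's own figure**

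Inputs: n = 120, assumed SVR12 96%, exact two-sided 95% interval, target lower bound above 91.5% (sections 10.1 and 10.3). The exact lower bound for x responders out of n is the 0.025 quantile of a Beta(x, n − x + 1) distribution.

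96% × 120 = 115.2. With x = 115 the bound is 90.5%; with x = 116 it is 91.7%. The planned bound is therefore reproduced only by rounding up to 116, that is, with at most 4 failures. This is a separate sample-size matter, but it explains why a single reclassified subject shows.

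**3. Effect of unbridged misses on the bound**

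Take 116 true responders among 120. Suppose k of them miss week 12 and count as failures. The documents give no rate of missed samples, so k is an assumption.

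| k | Counted responders | Exact lower bound |
|---|---|---|
| 0 | 116 | 91.7% |
| 1 | 115 | 90.5% |
| 2 | 114 | 89.4% |
| 3 | 113 | 88.4% |
| 4 | 112 | 87.3% |

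Each step costs about 1.1 points (91.69 − 90.54 = 1.15 for the first). If each of the k subjects were < LLOQ at weeks 4 and 24 and both results were available, the bound would stay at 91.7%.

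**4. Chance of reaching the planning target**

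Assume a true SVR12 of 96% and m subjects of 120 with no week-12 value, all counted as failures. The chance of at least 116 counted responders is P(X ≥ 116) with X ~ Binomial(120 − m, 0.96): 47% for m = 0, 29% for m = 1, 14% for m = 2, 5% for m = 3 and 0.9% for m = 4.

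The gap between a given m and m = 0 is the most that bridging could recover, not what it would recover. If m = 2 and one of the two returns at week 24 with the same 96% chance of satisfying the rule, the effective m is 1 and the chance moves from 14% to 29%. It reaches 47% only if both return.

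**The case against.** A reader might infer that the rule can never rescue SVR12 and that every missed week-12 sample must become a failure. The documents do not go that far. They say who will attend week 24; nothing bars anyone else. Sections 5.3 and 8.1.5 point to the flow chart for visit requirements, and it shows week 24 without the condition. The rule in 10.2 refers to values, not scheduled visits, so an unscheduled result below LLOQ would serve. All of this stands, and it limits the point to what the schedule guarantees. It does not remove the point: unscheduled visits depend on a request and their assessments are discretionary, and a flow chart that differs from three passages of text is itself an inconsistency to settle.

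A reader might also take the fall in step 4, for instance from 47% to 14% with two misses, as the cost of the current wording. That compares missing data with no missing data. The wording change helps only subjects who were below LLOQ at week 4, missed week 12, and return below LLOQ at week 24.

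Three further points are fair. Missing-as-failure is a conservative default for a single-arm rate. Section 10.2 says sensitivity analyses on missing data will be considered, although these cannot replace a sample that was never drawn. And 91.5% is not a pass/fail line: it is a precision target in 10.1, and 10.3 will interpret the bound irrespective of the sample-size assumptions.

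Nor do the documents show that the rule was written specifically to recover SVR12. It is general, and it works as scheduled for a missing SVR4.

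**Conclusion.** The point holds as a mismatch between the follow-up schedule and the missing-data rule. Under the synopsis and sections 8.1.5.3 and 8.1.5.3.2, no scheduled value follows a missing week-12 result, so SVR12 defaults to failure unless an unscheduled sample or a site's use of the flow chart supplies one. The direction of any bias is downward. Its size is about 1.1 points on the exact lower bound per sustained responder so classified, and near the planned result one such subject is enough to move the bound from above 91.5% to below it.

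The total effect depends on the number of isolated week-12 misses, which the documents do not give; it is nil if there are none. Subjects who never return are failures under either wording. The sponsor should settle this while follow-up can still be arranged.

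**What to change.** In the synopsis, section 8.1.5.3 and section 8.1.5.3.2, state that all treated subjects without confirmed virologic failure attend post-treatment week 24 with an HCV RNA sample, whether or not the week-12 sample was obtained. This brings the text into line with the flow chart, and the rule in 10.2 then works for SVR12 as written. The change concerns outcome sampling only.

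The cost is a wording change in three places and a few week-24 visits. These are already in the flow chart, and the budget in Annex 2 appears to cover them: nurse time is set at 0.25 h per visit and 2 h per patient, which is 2 / 0.25 = 8 visits, the full number in the flow chart.

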#### **8.1.5.3.1 Post treatment Week 4 (± 5 days)**

The following procedures are to be completed for all subjects, 4 weeks after taking the last dose of study drugs :

- Obtain body weight
- Obtain vital signs
- Assessment of AEs and concomitant medications
- Obtain blood samples for :
  - Hematology and chemistry

- HCV RNA
- Confirmation of birth control
- Obtain urine sample for :  
Beta-HCG pregnancy test for females of childbearing potential only

#### **8.1.5.3.2 Post Treatment Week 12 and 24 (+ 5 days)**

The following procedures are to be completed 12 and 24 weeks after taking the last dose of study drugs :

- Obtain body weight
- Obtain vital signs
- Assessment of AEs only related to study procedure
- Concomitant medications
- Obtain blood samples for :  
HCV RNA
- Confirmation of birth control
- Obtain urine sample for :  
Beta-HCG pregnancy test for females of childbearing potential only

Subjects with HCV RNA < LLOQ at the post treatment Week 12 Visit will return for the Post treatment Week 24 Visit

#### **8.1.5.4 Drug Administration**

Following completion of the Day 1 procedures and confirmation of eligibility, the site pharmacist or study coordinator will contact the Promotor for assignment of the drug to be administered.

Sites should not call the Promotor for drug administration until the subject has met all criteria for the study and is ready to receive the first dose of study medication on Day 1.

The first dose of prescribed study medications should be administered at the Day 1 visit. Subjects who discontinue therapy in the trial prior to the last scheduled treatment visit should have an Early Discontinuation visit and then continue with the follow-up visits.

At a minimum, collect the following information when a subject discontinues from the trial:

1. The reason the subject discontinued.
2. The date of the last dose of study medications from the trial.
3. The date of the last assessment and/or contact. A follow-up contact (telephone or visit) will be arranged as appropriate.

4. (Serious) Adverse events.
5. Final Assessments: Every effort should be made to ensure that all procedures and evaluations scheduled for the Early Discontinuation Visit are performed.
6. Retrieve all study medications from the subject.

#### **8.1.6 Evaluations of Laboratory Safety Signals**

Laboratory safety measurements will be evaluated weekly during the first 2 weeks, followed by monthly for the entire treatment period, and during the follow up period to assess potential liver safety signals as outlined in the flow chart.

If a subject has one or more of the laboratory ECI criteria (Refer section 8.1.3) at the last dosing visit then the subject should return to the site weekly for additional monitoring until the values normalize.

### **8.2 Assessing and Recording Adverse Events**

An adverse event is defined as any untoward medical occurrence in a patient or clinical investigation subject administered a pharmaceutical product and which does not necessarily have to have a causal relationship with this treatment. An adverse event can therefore be any unfavorable and unintended sign (including an abnormal laboratory finding, for example), symptom, or disease temporally associated with the use of a medicinal product or protocol-specified procedure, whether or not considered related to the medicinal product or protocol-specified procedure. Any worsening (i.e., any clinically significant adverse change in frequency and/or intensity) of a preexisting condition that is temporally associated with *the* use of the Sponsor's product, is also an adverse event.

Changes resulting from normal growth and development that do not vary significantly in frequency or severity from expected levels are not to be considered adverse events. Examples of this may include, but are not limited to, teething, typical crying in infants and children and onset of menses or menopause occurring at a physiologically appropriate time.

Sponsor's product includes any pharmaceutical product, biological product, device, diagnostic agent or protocol-specified procedure, whether investigational (including placebo or active comparator medication) or marketed, manufactured by, licensed by, provided by or distributed by the Sponsor for human use.

Adverse events may occur during the course of the use of the Sponsor's product in clinical trials or within the follow-up period specified by the protocol, or prescribed in clinical practice, from overdose (whether accidental or intentional), from abuse and from withdrawal.

Adverse events may also occur in screened subjects during any pre-allocation baseline period as a result of a protocol-specified intervention, including washout or discontinuation of usual therapy, diet, placebo treatment or a procedure.

All adverse events will be recorded from the time the consent form is signed through 14 days following cessation of treatment and at each examination on the Adverse Event case report forms/worksheets.

### **8.2.1 Definition of an Overdose for This Protocol and Reporting of Overdose to the Sponsor**

In this trial, an overdose is any dose higher than any intake in excess of prescribed dose per calendar day.

If an adverse event(s) is associated with (“results from”) the overdose of Sponsor's product the adverse event(s) is reported as a serious adverse event, even if no other seriousness criteria are met.

If a dose of Sponsor's product meeting the protocol definition of overdose is taken without any associated clinical symptoms or abnormal laboratory results, the overdose is reported as a non-serious Event of Clinical Interest (ECI), using the terminology “accidental or intentional overdose without adverse effect.”

All reports of overdose with and without an adverse event must be reported within 24 hours to the Sponsor either by electronic media or paper. Sponsor Contact information can be found in the Investigator Trial File Binder.

### **8.2.2 Reporting of Pregnancy and Lactation to the Sponsor**

Although pregnancy and lactation are not considered adverse events, it is the responsibility of investigators or their designees to report any pregnancy or lactation in a subject (spontaneously reported to them), including the pregnancy of a male subject's female partner that occurs during the trial or within 14 days of completing the trial. All subjects and female partners of male subjects who become pregnant must be followed to the completion/termination of the pregnancy. Pregnancy outcomes of spontaneous abortion, missed abortion, benign hydatidiform mole, blighted ovum, fetal death, intrauterine death, miscarriage and stillbirth must be reported as serious events (Important Medical Events). If the pregnancy continues to term, the outcome (health of infant) must also be reported.

Such events must be reported within 24 hours to the Sponsor either by electronic media or paper. Sponsor Contact information can be found in the Investigator Trial File Binder.

## **8.2.3 Immediate Reporting of Adverse Events to the Sponsor**

### **8.2.3.1 Serious Adverse Events**

A serious adverse event is any adverse event occurring at any dose or during any use of Sponsor's product that:

- Results in death;
- Is life threatening;
- Results in persistent or significant disability/incapacity;
- Results in or prolongs an existing inpatient hospitalization;
- Is a congenital anomaly/birth defect;
- Is a cancer;
- Is associated with an overdose;
- Is an other important medical event

Refer to Table 11 for additional details regarding each of the above criteria

Any serious adverse event, or follow up to a serious adverse event, including death due to any cause that occurs to any subject from the time the consent is signed through 14 days following cessation of treatment or within the established off therapy follow-up period for safety described in the protocol, whether or not related to the Sponsor's product, must be reported within 24 hours to the Sponsor either by electronic media or paper. Sponsor Contact information can be found in the Investigator Trial File Binder.

Additionally, any serious adverse event, considered by an investigator who is a qualified physician to be related to the Sponsor's product that is brought to the attention of the investigator at any time outside of the time period specified in the previous paragraph also must be reported immediately to the Sponsor.

All subjects with serious adverse events must be followed up for outcome.

